Efter opringning til Akuttelefonen 1813 vil forældre til børn i alderen 6 mdr. til 11,9 år blive tilbuddt at deltage. De vil blive informeret om, at de ved deltagelse får tilsendt et link til materialet på deres smartphone, og at de kan se materialet i 72 timer. De vil også få at vide, at ved deltagelse får de næste dag tilsendt et link til et SMS-spørgeskema med 6 korte spørgsmål, samt at deres barns journal igennem de næste 72 timer bliver læst, hvis barnet kommer på hospital. Der vil blive trukket lod om deltagelse. Forældrene der får materialet skal ringe 1813 igen, hvis de ønsker at tale med en sygeplejerske eller læge. Hvis de ikke får tildelt materialet kommer de til at tale med en sygeplejerske eller læge som vanligt.

Forskingsspørgsmålene vil blive besvaret udfri forældres svar på SMS-spørgeskemaet.

Første forskningsspørgsmål: Angav flere forældre, der fik adgang til materialet, høj grad af self-efficacy og empowerment end forældre, der ikke fik adgang til materialet?

Andet forskningsspørgsmål: a) Oplyste forældre, der fik adgang til materialet, i mindre grad, at deres børn var blevet undersøgt af læge end forældre, der ikke fik adgang til materialet, b) Angav forældre, der fik adgang til materialet, hyppigere høj grad af tilfredshed med kontakten til 1813 end forældre, der ikke fik adgang til materialet?

Samtlige projektdata vil blive fuldt anonymiserede, så det ikke på nogen måde er muligt at henføre data til personer. **Sikkerhed ved projektet** bliver undersøgt ved gennemgang af hospitalsjournaler af alle de inkluderede børn indenfor de næste 72 timer efter opkaldet. Ved utilsigtede hændelser vil en sikkerhedskomité tage stilling til om projektet skal afbrydes.

Det forventes, at forskningsspørgsmålene kan besvares indenfor en dataopsamlingsperiode på 3 mdr. Projektet vil ikke forløbe i længere tid end 6 mdr.

Appendix 1 viser hvorledes forældrene vil blive informeret om projektet og hvordan der vil blive indhentet informeret samtykke, samt de 6 SMS-spørgsmål der udsendes dagen efter opkaldet.

Introduction

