A Danish study from the Capital Region, in 2013 – the year before the medical helpline 1813 was introduced - found that 28% of the urgent consultations concerned 2.5% of the child population. These children had at least 4 urgent consultations yearly (6). Acute bronchitis was the most frequent diagnosis among these children, which were young (median age of 2.9 years), compared with all the children with an urgent contact (median age of 7.3 years) (6). Moreover, children with young mothers and children with immigrant parents had 37% and 28% increased risk for frequent contact (6), respectively.

A Danish study from the Capital Region, from 2014, the first year of the medical helpline 1813, showed that most calls concerned 0-1-year-old children who seldom exhibited serious conditions (7). The author interpreted the results as if the parents were primarily calling 1813 to get reassurance about the child's condition. When the children got older, the frequency of calls decreased, but in turn, they concerned more serious conditions (7).

Each year there are approximately 190,000 calls to the medical helpline 1813 regarding sick children younger than 12 years (injuries excluded) (8). These children are not so ill that the parents call the emergency helpline 112, but the parents need to contact the health care system outside their general practitioners' opening hours. After contact with the parents, the medical helpline 1813's health professionals may either: 1) refer the child to a paediatric department, 2) refer the

child to assessment in a paediatric urgent care centre (Børnelægevagten), 3) guide the parents to self-care at home, or 4) advised the child to their general practitioners (GP) the next workday.

In 2018, there were 192,000 calls about sick children (injuries excluded) (8). Of these calls, 57% children stayed at home the day the parents called 1813 (31% were guided in self-care and 26% were advised to their GPs the next workday), 40% were referred to the hospital (30% were referred to a paediatric urgent care centre and 10% were referred directly to a paediatric department) and 3% were referred to other options (8).

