Did the new material about sick children result in high parental self-efficacy among the parents who were allowed to watch the material?

Did new material about sick children result in less children examined by a doctor and more satisfied parents?

Primary outcome

Data of the electronic questionnaire from the parents;

High parental self-efficacy defined as parents who answered "i meget høj grad" or "i høj grad" to at least two of the three questions:

"Hvor godt kunne du passe dit syge barn hjemme, efter du søgte hjælp ved at ringe 1813?",
"Ved du hvad du kan gøre hjemme, hvis dit barn får samme symptomer en anden gang? and
"Ved du, hvornår det er så alvorligt, at du skal kontakte læge eller 1813, hvis dit barn får samme
symptomer en anden gang?"

Secondary outcomes

Data of the electronic questionnaire from the parents;

- Use of professional consultations: Yes to the question "Har en læge/sygeplejerske undersøgt dit barn under dette sygdomsforløb?" (både egen læge og læge på hospital).
- Satisfied with the contact to the acute telephone 1813: Yes (svar "i meget høj grad" og "i høj grad") to the question "Er du overordnet tilfreds med den hjælp du fik, da du kontaktede 1813?"

Exploratory outcomes

Data of the electronic questionnaire from the parents;

- The medical status of the sick child "Hvordan har dit barn det nu, sammenholdt med da du kontaktede 1813?"

Data from the Copenhagen Emergency Services;

- The number of telephone contacts to 1813, the age and the sex of the child.
- The number of parents who called 1813 within the next 72 hours after the initial call.
- The number of patients, who were referred to a hospital within the next 72 hours after the initial call.

Data of the calls from the videos and action cards;

- The number of times the 8 videos and the eight action cards were used within the next 72 hours after initial contact to 1813.
- The duration and types of videos and action cards the parents watched within the next 72 hours.

Data from the case reports from Epic (Sundhedsplatformen);

- The number of patients, who went to a hospital within the next 72 hours after the initial contact to 1813, and the time of arrival.
- The number and diagnoses of patients who did neither get treatment nor paraclinical tests, but merely parental medical at hospital.
- The number and diagnoses of patients who went home from the hospital with treatment for example antibiotics or painkillers.

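### The secondary outcome on professional examination does not match its own aim: the aim is about examination by a doctor, but the scored SMS item counts a doctor or a nurse

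*Combined protocol and SAP*

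**What the plan says.** Five pieces of text in the combined protocol and SAP describe this outcome.

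- **Aim of the study**, second question: "Did new material about sick children result in less children examined by a doctor and more satisfied parents".
- **Danish summary**, second research question, part a: whether parents given the material report "i mindre grad, at deres børn var blevet undersøgt af læge end forældre, der ikke fik adgang til materialet", that is, less often report examination by a doctor than parents without access.
- **Secondary outcomes**, label: "Use of professional consultations".
- **Secondary outcomes**, scored item: a yes to "Har en læge/sygeplejerske undersøgt dit barn under dette sygdomsforløb" (has a doctor/nurse examined your child during this illness).
- **Secondary outcomes**, note after the item: "både egen læge og læge på hospital" (both own GP and hospital doctor).

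The Statistics section tests the primary outcome at two-sided p<0.05 and each of the two secondary outcomes at p<0.025. Everything else is exploratory and is not to support an efficacy claim.

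The Danish summary also describes what happens on the call. For controls: "Hvis de ikke får tildelt materialet kommer de til at tale med en sygeplejerske eller læge som vanligt" (they speak to a nurse or doctor as usual). For the intervention arm: "Forældrene der får materialet skal ringe 1813 igen, hvis de ønsker at tale med en sygeplejerske eller læge" (they must ring again if they want to do so).

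**The concern.** The aim asks about doctors, while the variable that will be analysed covers doctors and nurses. The visible text does not say how a child seen only by a nurse should be classified: the item says yes, and the aim, research question and note say no. The answer is a single yes or no, so nurse-only replies cannot be separated once the data are in.

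This is the only measure of health-care use with its own test level, and reducing unnecessary attendance is part of the trial's rationale. If the plan is followed exactly, the test answers a different question from the one posed, and the wording of the claim would be settled after the result is known.

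A smaller, related point is that the item names the same two professions that controls speak to by telephone, and no visible text says that the telephone contact does not count.

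**Working it through.** **Test level.** The plan's figure for each secondary outcome is 0.025. An equal split of 0.05 over two outcomes gives 0.05/2 = 0.025, which matches, although the plan does not name the method. The mismatch changes neither this level nor the sample size.

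**How each text treats a child examined only by a nurse.**

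| Text | Who examines | Nurse-only child |
|---|---|---|
| Aim of the study | doctor | not counted |
| Danish research question | doctor | not counted |
| Note after the item | own GP, hospital doctor | not named |
| Label | unspecified professional | fits |
| Scored item | doctor or nurse | counted as yes |

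The scoring rule is a yes to the item, so the last row decides what is analysed.

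**What the item estimates.** In arm k, let D_k be the proportion examined by a doctor and N_k the proportion examined by a nurse only. The item measures D_k + N_k, so

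item difference = (D_I − D_C) + (N_I − N_C).

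The aim concerns the first bracket only. If N_I = N_C the second bracket is zero, and the difference in proportions is the one the aim asks about. If the nurse-only shares differ between arms, the item and the aim diverge.

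**Size.** The documents give no rate for doctor, nurse-only or combined examination, so the actual effect cannot be computed. The following rests entirely on assumed rates and shows only when the definition matters.

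- Assumptions: doctor examinations 40% in controls and 35% in the intervention arm; two-sided 0.025 (z = 2.241); 3300 or 2520 replies in total, the plan's two sample sizes; equal arms.
- Formula: power = Φ[(d − z × SE0)/SE1], with d the difference in proportions, SE0 the pooled and SE1 the unpooled standard error.
- Doctor only, 1650 per arm: SE0 = √(2 × 0.375 × 0.625/1650) = 0.016855; SE1 = √((0.24 + 0.2275)/1650) = 0.016833; (0.05 − 2.241 × 0.016855)/0.016833 = 0.726; power 77%. With 2520 replies, 64%.
- An equal nurse-only share of 5% to 20% added to both arms: 74% to 75% with 3300 replies, 61% to 62% with 2520. Little changes.
- If half of the 5-point reduction becomes nurse examinations, the item difference is 2.5 points. Over a common nurse-only share of 0 to 20%, power is 21% to 22% with 3300 replies and 16% to 17% with 2520.

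The definition is nearly harmless if nurse-only examinations are rare or balanced. It matters if they replace doctor examinations. The documents do not say which holds.

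**Telephone contact.** The Danish summary has all controls speaking to a nurse or doctor, and intervention parents doing so only if they ring again. Any parent who counts the call as an examination would therefore be found mainly among controls, which would favour the intervention. The direction follows from the text. The size does not, because the documents give neither a misreading rate nor a call-back rate.

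**The case against.** The outcome can be scored as written. A yes to one item is unambiguous, and two analysts would build the same variable. That stands, but it settles what is scored and not whether the score answers the aim.

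The note after the item could be read as listing settings (general practice and hospital) rather than excluding nurses. That is possible, but it names a doctor in both settings, and the aim and research question are doctor-only in any case.

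The Introduction lists four dispositions after a call to 1813, and none is described as a nurse-only examination, so the share may be close to zero. This stands as a limit on the size of the problem. Hospital attendance, hospital referral and repeat calls are also recorded independently of the questionnaire, although they do not cover GP visits.

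A reader might go further and infer that the control arm's telephone contact biases the test and inflates its false-positive rate. The documents do not support that. The item asks whether the child was examined, which a telephone call is not. The page of Appendix 1 with the SMS items was not in the text available, so what parents actually read cannot be judged. The 2018 figures in the Introduction ("26% were advised to their GPs the next workday), 40% were referred to the hospital") do not supply an examination rate: they count referrals and advice rather than examinations, they cover all sick-child calls under 12 years rather than consenting parents of children from 6 months, and they arise after contact with 1813 staff, whom intervention parents reach only by ringing again. No false-positive figure should be quoted.

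**Conclusion.** The mismatch is certain from the text. The aim and research question specify a doctor, the note names only doctors, and the scored item admits a nurse. A result on this item, significant or not, cannot be reported as a finding about children examined by a doctor.

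The consequence is limited. Only one secondary outcome is affected. The nurse-only share is unknown and may be small. A reader might infer that counting nurse-only children creates a spurious difference; equal counting in both arms does not, although it changes what is measured. The possible misreading of the telephone call would favour the intervention, but its size cannot be estimated, so it justifies a safeguard in the wording and nothing stronger. Severity: minor to moderate.

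**What to change.** Before enrolment, bring aim, research question, label, item and note to one definition.

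- **Preferred:** word the item and its label, and the SMS text in Appendix 1 if it is not already so worded, as whether a doctor (own GP or at hospital) has examined the child in person, with telephone contact with 1813 not counted. Three of the five texts already speak of doctors, so only the item and label change.
- **Alternative:** keep doctor or nurse in the item, widen the aim, research question and note to match, bring the label into line, and add the same telephone exclusion. This also removes the conflict but changes the stated research question.

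The telephone exclusion is worth including under either option, since the arms differ by design in who speaks to a nurse or doctor on the call.

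The cost is a few words in one SMS item and its label, or in the aim, research question, note and label, with no new data collection and no change to the test level or sample size. The downside of the preferred wording is that nurse-only examinations are no longer counted.

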Is it possible – by using videos and simple action cards about common symptoms in children - to empower parents and citizens to take better care of children with milder symptoms at home and to know when to go to a doctor or hospital? The project will help the parents be empowered so they are more confident about caring for their sick children including to know when it is needed to call for help. Competence in caring for children and safety are important aspects of a good family life.

The project addresses a current challenge in the public health sector since many children are referred to hospitals outside their general practitioners' opening hours, and many of these children exhibit only mild symptoms which require neither treatment nor paraclinical tests, but merely medical parental guidance. The project utilises appropriate means, since most parents value the Internet as an information resource. Thus, the material will meet the users where they are – online on their smartphones.

The nature of the problem: a lot of 'trivial' illness in children

Up to the age of four years, children have from 23 to 80 days of sickness a year, where they couldn't play normally, most days of sickness for children attending day care (1-4). In average the parents reported that the child had had 3.3 episodes of sickness a year and that each period of sickness lasted next to 7 days (4). It may be scaring for parents when their child gets sick, especially when it is for the first time. In about 50% of these contacts, the parents felt the child needed treatment, but in less than 10% of the cases they felt the child was seriously ill (4). Parents with only one child had most medical calls. For children with one or two siblings, doctor's contact was reduced by one third, when compared to first born children, and for children with of three or more siblings' it was reduced to less than one tenth (4). As the average number of children per Danish women is 1.75 only (5), many children are the first-born child.

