If we suggest that 25% of the parents to the sick children agree to be randomized, and that 40% of the included parents answers the text-message the next day, then we can include $(160,000 \times 0.25)/365 =$ about 110 children a day, and we will get about 44 text-messages a day. Then we need $2520/44 - 3300/44 = 57- 75$ days to include enough patients. It is less than 3 months.

In the data from the Copenhagen Emergency Services, and data from the safety measures we will not have loss to follow up, since data from the Copenhagen Emergency Medical Services and from all four Departments of Paediatrics in the Capital Region are collected routinely.

In the data of the calls from the cases we also suggest that all contacts are safety stored so we will have no loss to follow-up.

We suggest we have data to answer our research question within 3 months, and the study will be stopped after 6 months.

Stop of the study before an answer our research question

In cases of serious adverse events the study group will consider stopping the study. This will also be the case if the satisfaction with the contact to the acute telephone 1813 drops to a very low level.

Statistics

The primary analysis will use Chi-square and a two-sided level of significance of $p < 0.05$ for the primary outcome and a $p < 0.025$ for the two secondary outcomes. All other outcomes are exploratory and the statistical methods will be adapted as appropriate. The results from these exploratory analyses will not be used to claim clinical efficacy but used to design new studies. This is an important aspect since new studies can be rapidly designed and performed once the project set-up is in place.

The dataset will be rich and allow exploration of the effect of individual videos, as well as subgroup analyses.

We believe that our set up is robust, as the sick children are included based on electronic equipment, not adding extra work on the medical personnel, the operators. The follow up to the parents by text message the next day is also based on electronic equipment and the follow-up in the medical case reports after 72 hours, for safety reasons, is based on easily available information, if we have the relevant permits for this.

Ethics and transparency

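### The consultation outcome has no start point at the 1813 call, so examinations before randomisation score as events; this creates no false benefit, but it can hide an effect, by an unknown amount

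*Combined protocol and SAP*

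**What the plan says.** Under Secondary outcomes, use of professional consultations is scored from one SMS item: "Har en læge/sygeplejerske undersøgt dit barn under dette sygdomsforløb". A bracket adds "både egen læge og læge på hospital", so visits to the child's own GP count as well as hospital examinations. The Danish summary puts the research question in similar terms, again without a start point: "Oplyste forældre, der fik adgang til materialet, i mindre grad, at deres børn var blevet undersøgt af læge". The aim it serves is causal: "Did new material about sick children result in less children examined by a doctor and more satisfied parents".

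Under Set up, parents are randomised when they call 1813 about a child who is already sick. The listed exclusions concern language, telephone or smartphone, injury, and participation within the last 72 hours. The SMS goes out the next day, at least 12 hours after the call, with one repeat to those who have not answered. Under Statistics, the outcome is tested by chi-square at "a $p < 0.025$ for the two secondary outcomes".

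Other outcomes are tied to the call. The first self-efficacy item reads "Hvor godt kunne du passe dit syge barn hjemme, efter du søgte hjælp ved at ringe 1813", and an exploratory outcome is "The number of patients, who went to a hospital within the next 72 hours after the initial contact to 1813, and the time of arrival".

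**The concern.** The item covers the whole illness, and the illness began before the call. A parent whose child saw the GP two days earlier must answer Yes, whichever arm the family is in and whatever happens afterwards. The aim can be answered only by examinations after randomisation.

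Prior examinations are plausible. The helpline serves families outside GP hours, GP visits count, and the background section says that "each period of sickness lasted next to 7 days". No listed exclusion, baseline item or analysis step separates these children from the rest. At stake is the reading of one of only two secondary outcomes that are formally tested, and the one closest to the project's rationale of sparing families unnecessary visits. A null result could reflect the wording of the item instead of the material.

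**Working it through.** **1. The plan's own sample size.** The trial is sized on the primary outcome only, at two-sided 0.05 and 80% power. For 50% vs 55%, the standard two-proportion formula gives 3130 replies in total, or 3210 with continuity correction, against about 3300 stated. For 70% vs 75% it gives 2502 or 2582, against 2520 stated. The stated figures are reasonable, and this point does not rest on them. They supply the replies per arm: 3300/2 = 1650 and 2520/2 = 1260.

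**2. What the item measures.** Let q be the share of children examined before the call, equal in both arms in expectation. Let p be the post-call examination rate among children not yet examined. Then

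P(Yes) = q + (1 − q)p, and the observed difference = (1 − q)(p_control − p_material).

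Post-call differences among children already examined drop out, because those children are all Yes. What is lost therefore depends on how much of the effect lies in them.

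**3. Assumptions.** The documents give neither q nor an effect size for this outcome. I take q = 10, 20 and 30%, a post-call control rate of 40%, and a true difference of 6 points over all children (40% vs 34%, risk ratio 0.85). The 40% is only a proxy: it is the share of 2018 calls referred to hospital. Two cases bracket the question:

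- Case A: the effect is the same in children already examined. The observed difference is 6(1 − q) points.
- Case B: the whole effect lies in children not yet examined, so p_control − p_material = 6/(1 − q) points among them. The observed difference stays at 6 points.

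**4. Power.** With n per arm and two-sided alpha 0.025 (z = 2.241),

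power = Φ[(d − 2.241·SE0)/SE1], where SE0 = √(2p̄(1 − p̄)/n) and SE1 = √((p1(1 − p1) + p2(1 − p2))/n).

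Example, case A, q = 20%, n = 1650: control 0.20 + 0.80×0.40 = 0.520; material 0.20 + 0.80×0.34 = 0.472; d = 0.048; SE0 = 0.01741; SE1 = 0.01739. Then (0.048 − 0.03902)/0.01739 = 0.517, and power is 70%.

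| q | Case A rates | Diff. | RR | Power 1650 / 1260 | Case B rates | Diff. | RR | Power 1650 / 1260 |
|---|---|---|---|---|---|---|---|---|
| 0% | 40.0 vs 34.0 | 6.0 | 0.85 | 91% / 81% | 40.0 vs 34.0 | 6.0 | 0.85 | 91% / 81% |
| 10% | 46.0 vs 40.6 | 5.4 | 0.88 | 81% / 69% | 46.0 vs 40.0 | 6.0 | 0.87 | 89% / 79% |
| 20% | 52.0 vs 47.2 | 4.8 | 0.91 | 70% / 57% | 52.0 vs 46.0 | 6.0 | 0.88 | 89% / 78% |
| 30% | 58.0 vs 53.8 | 4.2 | 0.93 | 57% / 45% | 58.0 vs 52.0 | 6.0 | 0.90 | 89% / 78% |

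If q is only 5%, case A power with 1650 per arm is 86%. With a 5-point effect instead (40% vs 35%), case A power with 1650 per arm is 77, 64, 52 and 41% for q = 0, 10, 20 and 30%.

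**5. What holds in both cases.** Both reported rates rise and the risk ratio moves towards 1. The absolute difference and most of the power are lost only in so far as the material also works in children already examined.

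**The case against.** Four points count on the other side.

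The questionnaire itself is not visible. The protocol refers to Appendix 1 for the SMS questions, and those are missing from the copy reviewed. A lead-in or an earlier item could tie the question to the call. This stands as a limit on certainty, although the outcome definition in the body of the protocol quotes the item and contains no such anchor.

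A reader might infer that the wording necessarily shrinks the difference by the factor (1 − q), or that power will drop to 57%. The documents do not support that. Adding equal numbers of Yes answers to both arms leaves an absolute difference unchanged; shrinkage needs an effect in children already examined, and nothing says whether there is one. The share q may also be small. The 7-day figure is a total duration, in text about children up to four years, and does not show how late in an illness parents call.

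A reader might also suspect a bias in favour of the material. Randomisation makes prior examinations equally likely in both arms, so no false benefit is expected.

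Finally, hospital attendance within 72 hours is recorded with time of arrival and counted from the call, and the plan expects no loss to follow-up there. This is a real cross-check but a partial one: it is exploratory, the plan says exploratory results will not be used to claim efficacy, and it misses GP visits.

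**Conclusion.** The point holds as a defect in how a tested secondary outcome is defined. As written, examinations before randomisation count as events, and the plan does nothing to separate them. The direction is clear: higher rates in both arms, a risk ratio closer to 1, and possible masking of a real effect. The size is not known. Under the assumptions shown, with 1650 replies per arm, power falls from 91% to between 81% and 57% in the unfavourable case, and only to about 89% in the favourable one. The documents do not say which case is nearer the truth. No power was promised for this outcome, and the primary outcome and stated sample size are untouched. It merits correction because correction is nearly free, not because a large loss has been shown. Confidence is moderate, given that Appendix 1 could not be checked.

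**What to change.** Before launch, replace the phrase about the course of illness in the SMS item with *efter du ringede til 1813* (after you called 1813). Define the secondary outcome as examination by a doctor or nurse after the index call. Check that the item in Appendix 1 and the research question in the Danish summary say the same. If Appendix 1 already carries such an anchor, copy it into the outcome definition.

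The cost is one changed SMS question and matching text, with no extra data collection, staff or participants. It should be done before the first SMS is sent, because afterwards Yes answers cannot be divided into before and after the call from the SMS data.
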